The protocol, informed consent form(s), recruitment materials, and all participant materials will be submitted to the IRB for review and approval. Approval of both the protocol and the consent form must be obtained before any participant is enrolled. Any amendment to the protocol will require review and approval by the IRB before the changes are implemented to the study. All changes to the consent form will be IRB approved; a determination will be made regarding whether a new consent needs to be obtained from participants who provided consent, using a previously approved consent form.

1 PROTOCOL SUMMARY**1.1 SYNOPSIS****TITLE:**

The Effect of Camostat Mesylate on COVID-19 Infection in Ambulatory Patients: An Investigator-Initiated Randomized, Placebo-Controlled, Phase IIa Trial

Study Description:**Objectives:**

Primary Objective: To determine whether camostat mesylate reduces SARS-CoV-2 viral load in early COVID-19 disease.

Secondary Objective: To determine the effect of camostat mesylate on COVID-19 symptom score.

Endpoints:**Primary Endpoint:**

1. Change (reduction) from baseline to day 4 in respiratory (Nasopharyngeal swab, saliva RT-PCR) \log_{10} viral load.

Secondary Endpoints:

1. Change (reduction) from baseline to day 2 and to day 6 in respiratory (Nasopharyngeal swab, saliva RT-PCR) \log_{10} viral load.
2. Difference in rate of a positive COVID-19 test result at day 6, 14 and 28 after enrollment
3. Change of COVID-19 symptom score from baseline to day 6 and to 14
4. To assess the safety of camostat mesylate 200 mg po QID

Exploratory Endpoints:

[figure not shown]
1. Conversion of SARS-CoV-2 antigen detection (Quidel's Sofia assay) from Nasopharyngeal specimens from baseline to days 6 and 14; there is no specific *a priori* power analysis for this exploratory outcome because this assay is new (under an FDA EUA) and has not been used for serial assessment of outpatients and this exploratory analysis will provide data regarding the performance of this test in our outpatient context.

2. To gain insight into whether clinical outcomes might improve after treatment with camostat mesylate 200 mg po QID but this study is not powered to assess progression to hospitalization or other severe disease.

Population:	Male and female outpatients 18 and older with RT-PCR-confirmed COVID-19 recruited and enrolled from Yale New Haven Health System or referred/presenting for the study because of a positive COVID-19 test from an outside clinical laboratory. The subjects will not be stratified, hence will be undifferentiated as to general health status or geographic location.
Phase:	2
Description of Sites/Facilities	Yale New Haven Health System
Enrolling Participants:	
Description of Study	Camostat mesylate 200mg po QID or placebo for 7 days
Intervention:	
Study Duration:	1 year
Participant Duration:	4 weeks

1.2 SCHEMA

See below.

Flow diagram of randomized controlled trial

1.3 SCHEDULE OF ACTIVITIES (SOA)

Procedures	Enrollment, Study Visit 1, Day 0	Study Visit 2 Day 2	Study Visit 3 Day 4	Study Visit 4 Day 6	Study Visit 5 Day 14+/- 2 days	Study Visit 6 Day 28+/- 2 days
Informed consent	X					
Demographics	X					
Medical history	X					
Randomization	X					
Administer study intervention: Subjects receive two days worth of drug/placebo on days 0, 2, 4 and one day of drug/placebo on day 6	X Drug/placebo For 2 days	X Drug/placebo For 2 days	X Drug/placebo For 2 days	X Drug/placebo For 1 day		
Nasopharyngeal swabs, saliva for COVID-19 RT-PCR and antigen testing	X	X Swabs optional	X	X Swabs optional	X	X
Physical exam: Vital signs, wt, pulse oximetry, other as clinically indicated	X	X	X	X	X	X
Urine pregnancy test (as indicated)	X					
Blood pregnancy test (as indicated)					X	
Hematology and coagulation	X				X	X
Blood chemistries	X				X	X
Adverse event review and evaluation	X	X	X	X	X	X
Concomitant medication review	X	X	X	X	X	X
Blood for research biorepository	X				X	X
Complete Case Report Forms (CRFs)	X	X	X	X	X	X

All subjects, regardless of study arm (blinded to subjects and investigators), will be tracked for their health status through daily phone calls from days 0 to day 14 with routine, scheduled daily phone calls by study staff to help participants fill out symptom scores on the standardized COVID-19-PRO instrument. Any subject reporting concerning symptoms, particularly chest pain, shortness of breath, extreme prostration, change in mental status will be referred to for emergency care. Subjects will be given a contact phone number of PI or designee to contact for any concerns. If there is complete resolution of symptoms at the day 14 visit, then phone calls will not be routinely continued by our study staff but subjects will be encouraged to call PI or designee for concerns or discussions.

2 INTRODUCTION

2.1 STUDY RATIONALE

SARS-CoV-2, one of a family of human coronaviruses, was initially identified in December 2019 in Wuhan city.¹ This new coronavirus causes a disease presentation which has now been named COVID-19. The virus has subsequently spread throughout the world and was declared a pandemic by the World Health Organization on 11th March 2020. In the United States, as of 12 April 2020, there were 532,339 confirmed cases with 21,418 deaths, with an estimated case-fatality rate of 4% for identified cases. At this time, there is no approved specific treatment for COVID-19 nor any drug or vaccine that could be used to prevent COVID-19. The current standard of care is limited to supportive treatment. The rationale of the present clinical trial is that an orally available drug given to outpatients that could reduce the viral burden in the upper respiratory tract could forestall complications of SARS-CoV-2 infection and reduce transmission from one infected individual to another.

Success in this trial, which focuses on the biological outcome of reduced viral load in the respiratory tract, would then lead to scaled-up clinical trials, for treatment in hospital inpatients and as prophylaxis for those at risk for infection. Alternatively, if camostat mesylate does not reduce viral load in the respiratory tract, then this drug would not be pursued for further clinical study.

2.2 BACKGROUND

Introduction

SARS-CoV-2, one of a family of human coronaviruses, was initially identified in December 2019 in Wuhan city.² This new coronavirus causes a disease presentation which has now been named COVID-19.³ The virus has subsequently spread throughout the world and was declared a pandemic by the World Health Organization on 11th March 2020. In the United States, as of 12 April 2020, there were 532,339 confirmed cases with 21,418 deaths, yielding an estimated case-fatality rate of 4% for identified cases (which is surely an underestimate). Therapy for COVID-19 and the current standard of care is supportive treatment.

Patients infected with SARS-CoV can present with a range of symptoms from asymptomatic infection to severe respiratory failure, septic shock and multiple organ failure.³ The most common symptoms are fever, cough, myalgia and dyspnea, though some patients present with headache, dizziness, nausea and vomiting. Viral pneumonia occurs in severe disease and leads to severe acute respiratory failure. Overall estimation of mortality rates vary from 0.039 and 7%, depending on the efficiency of population-based RT-PCR testing and host demographic and baseline clinical status.

SARS-CoV-2 uses the angiotensin converting enzyme II (ACE2) as its cell entry receptor protein to access and infect human cells.⁴ The interaction between ACE2 and the spike protein is not in ACE2's active site. This process critically uses the human epithelial cell (respiratory, gastrointestinal tract) surface-expressed serine protease TMPRSS2.⁴ Utilizing previous research on severe acute respiratory syndrome coronavirus (SARS-CoV) and the closely related SARS-CoV-2 cell entry mechanism, it has been demonstrated that SARS-CoV-2 cellular entry can be blocked by camostat mesylate (Folpan, Ono Pharmaceuticals) *in vitro*.⁵ *In vivo*, using a strain of SARS-CoV-1 adapted to causing lethal disease in a mouse model, camostat mesylate dosed at a concentration similar to the clinically achievable concentration in humans reduced mortality following SARS-CoV infection from 100% to 30-35% in this model.

Rationale for choice of study drug

Camostat mesylate is a proteolytic enzyme inhibitor that is used primarily in the treatment of postoperative reflux esophagitis and for acute, symptomatic exacerbations of chronic pancreatitis.⁵ It has been used clinically since at least 2006 and is widely used in Japan for chronic-pancreatitis associated pain. Importantly, camostat mesylate is very well tolerated and has no known drug-drug interactions.

This randomized controlled trial will investigate the clinical effect of camostat mesylate on viral kinetics of SARS-CoV-2 in newly diagnosed COVID-19 in ambulatory patients. There are two arms named A and B. Arm A is the camostat mesylate arm which will provide drug in identical appearance as placebo by overencapsulation. Patients in group A will receive 200 mg camostat mesylate to be taken four times daily. Arm B is the placebo arm and will be given YNHH research pharmacy-formulated placebo 4 times a day. All patients will receive treatment or placebo for a total of 7 days.

There is no clinical experience in using camostat mesylate in humans to treat SARS-CoV-2. Camostat mesylate, approved for clinical use in Japan since 2006, has been used there for more than two decades to treat reflux esophagitis and acute-on-chronic pancreatitis, and it displays very little toxicity (detailed below). In animal studies, treatment with comparable human dosing reduces mortality (100% to 35% within the study period of 13 days) in mice exposed to SARS-CoV.

[figure not shown]
[figure not shown]

Figure 1. Camostat mesylate inhibits TMPRSS2-mediated priming of the SARS-CoV-2 spike protein which prevents the virus from cell entry. *Adapted from Clerkin et al. Circulation 2020*

In another study, camostat was found to have an EC₅₀ of 87nM *in vitro*, a peak concentration achievable with oral camostat mesylate administration.⁶

Camostat mesylate is immediately and extensively hydrolysed in plasma to 4-(4-guanidinobenzoyloxy)phenylacetic acid (GBPA (FOY-251)), which is further degraded to 4-guanidinobenzoic acid (GBA). CM and GBPA have similar biological activity, while GBA is inactive.

Indication of absorption fraction after oral dosing is not available.

The Japanese manufacturer's summary of product characteristics describes a study in five healthy, fasting adults of a single oral dose of 200 mg. For GBPA Tmax is 40 min, Cmax 87.1 ng/ml, AUC 10,400 ng*min/ml and T_{1/2} 100min. Another study of four patients with complete gastrectomy given a single dose of 100 mg shows similar plasma curve changes including Cmax 30 ng/ml.

[figure not shown]
In another study, four healthy Caucasian males received a single dose of 40 mg camostat mesylate as intravenous infusion over 12 hours. The parent compound was not measurable in plasma, supportive of instantaneous degradation. PK parameters for the active metabolite, GBPA, were T_{max} 300 min (after infusion start), C_{max} 89.4 ng/ml, C_{ss} 83.6 ng/ml, AUC 966 ng.h/ml and T_{1/2} 1.0 hrs.

In a study of pancreatic function, twelve healthy individuals (6M/6F, median age 24.5 yrs) were given 500 mg four times daily for four weeks. Steady state concentration for GBPA at the end of week 1-4 were 19,600 ng/ml, 18,600 ng/ml, 19,000 ng/ml and 14,400 ng/ml.

Camostat mesylate is almost exclusively metabolized to GBPA and further on to GBA, by carboxyesterase and arylesterase. Neither parent compound nor metabolites affect CYP1A2, CYP2C9, CYP2C19, CYP2D6 or CYP3A4. Excretion is mainly renal as GBA (>95%).

The main metabolites of CM are renally eliminated, predominately 4-guanidinobenzoic acid (GBA) and to a much lesser extent 4-(4-guanidinobenzoyloxy)phenylacetic acid (GBPA). After a single oral administration of 200 mg in 5 healthy adults, the majority of these metabolites were excreted after 5-6 hours¹⁰. No PK studies have been located that have included patients with chronic kidney disease. However, the TACTIC trial, recruiting patients aiming at investigating the effect of CM against chronic pancreatitis in a western population, excludes patients with CKD stage IV (eGFR < 30 ml/min/1,73m²)¹⁵. This suggests that prior studies could potentially have documented the safety of CM use in patients with milder degrees of renal impairment.

In PK simulation modeling provided recently by Ono Pharmaceuticals, the new FDA suggested dosing of 200 mg QID of camostat would yield the following curves and time of blood levels exceeding the 87 nM EC₅₀.

Interactions with other drugs

There are no known interactions with other drugs and CM, GBA, GBPA. The drug and metabolites are not dependent on CYP metabolism.

Camostat mesylate is a serine protease inhibitor. The protease transmembrane protease serine S1 member 2 (TMPRSS2) activates the spike protein of the severe acute respiratory syndrome coronavirus (SARS-CoV) on the cell surface, and camostat inhibits TMPRSS2-dependent infection by SARS-CoV.⁴

According to the SmPC camostat is indicated for: Remission of acute symptoms of chronic pancreatitis (CP) 600 mg day/Postoperative reflux esophagitis (RE) 300 mg day. 3806 patients were evaluated in the Drug Use Investigation and observed for adverse reaction. The following has been reported.

Adverse Reactions (also shown in Table 1)

Abnormal laboratory test (1.3-1.8%), hepatic function abnormalities (Increased AST, ALT – 0.3%), Rash (0.4%), Pruritus (0.2%), nausea (0.1-0.3%), abdominal discomfort (0.2%), diarrhea (0.2%).

Clinical significant adverse reactions: (incidences unknown, thus rare)

- Shock and anaphylactic symptoms (decreased blood pressure, dyspnea, pruritus)
- Thrombocytopenia
- Hepatic function disorder or jaundice
- Hyperkalemia

Reported adverse effect are rare (<3%) and typically mild (such as pruritus, increased thirst and appetite and lightheadedness).

A phase 1/2 study was designed to study camostat mesylate as a treatment for chronic pancreatitis in the United States. The phase I study, investigated the pharmacokinetics and safety of 100, 200 and 300 mg doses and demonstrated safety in 18 subjects.⁷ The phase 2 study was a double-blind, randomized, parallel-group, dose-ranging study and is underway to further assess the safety and efficacy of camostat versus placebo. May 2019: 63 subjects have completed the study out of 78 subjects enrolled into phase 2. A total of six serious adverse events (SAEs) have been reported in three subjects; none of these events were dose-limiting toxicities. In all but one case, the SAEs occurred during the follow-up period and none were considered related to study treatment. Only one subject has withdrawn due to an adverse event of nausea/vomiting while on treatment, which was considered as possibly related to treatment.

Adverse Reactions	0.5 – 0.1%	<0.1%	Incidence Unknown*
Hematologic	-	Leukopenia Erythropenia	Eosinophilia
Hypersensitivity	Rash Pruritus	-	-
Gastrointestinal	Nausea Abdominal discomfort Abdominal fullness Diarrhea	Anorexia Vomiting Dry mouth Heartburn Abdominal pain Constipation	-
Hepatic	Increased AST, ALT, etc.	-	-
Renal	-	Increased Blood Urea Nitrogen (BUN) Increased Creatinine	-

Others	-	Edema	-
		Hypoglycemia	

Table 1. Summary of Safety Data for Camostat Mesylate tablets

Data summarized from the use of camostat mesylate for the indications of "Remission of acute symptoms of chronic pancreatitis" (83 ARs including abnormal lab.values observed in 69 (1.8%) of 3,806 patients) and "Postoperative reflux esophagitis" (75 ARs including abnormal lab.values observed in 57 (1.3%) of 4,224 patients).

Additional clinically significant ARs that may occur (incidences unknown*):

Shock or anaphylactoid symptoms, thrombocytopenia, hepatic function disorder or jaundice, hyperkalaemia.

*Incidence unknown: ADRs classified and collected from spontaneous reports.

Two case reports have been found. One about autoimmune hepatitis that may have occurred following drug-induced liver injury that may have been related to camostat treatment. Stopping the drug did not lead to complete remission, but low dose of corticosteroids completely cured the liver function¹⁷. Another case study reported eosinophilic pneumonia probably caused by 10 days treatment with camostat. The peripheral blood eosinophilia and eosinophilic infiltration into the alveolar space improved with the cessation of the drug¹⁸.

Relevant monitoring of treatment is based on the knowledge about the reported clinically significant adverse reactions, which comprises: hyperkalemia, hepatic function disorder or jaundice, thrombocytopenia, eosinophilic pneumonia and shock/anaphylactic symptoms.

Safety in patients with reduced renal output or end-stage renal disease

Human data on camostat mesylate treatment and renal insufficiency.

Three studies have been found in Medline and/or Embase that address the safety of camostat mesylate administration in patients with renal insufficiency:

1. Onbe et al. J Diabet Complications 1991;5:167-8. 8 pts with nephrotic syndrome and diabetic nephropathy. CM 600 mg daily for 4 weeks. Reduced proteinuria, creatinine clearance stable throughout study.

2. Ikeda et al. J Diabetes Complications 1999;13:56-8

3 pts with nephrotic syndrome and diabetic nephropathy. CM 600 mg daily for 4 weeks. Reduced proteinuria, no side effects reported.

3. Matsubara et al. Clin Nephrol 1989;32:119-23

17 pts with heavy proteinuria caused by varous nephropathies. CM 600 mg daily for 4 weeks. Urine protein excretion diminished from week 2. No changes in serum creatinine during or after the study.

Collectively, the above-mentioned studies demonstrate the safety profile of camostat mesylate administration in patients with varying degrees of renal insufficiency. The studies found no evidence of a negative effect of camostat mesylate on renal function. Camostat mesylate administration was also not associated with an increased risk of adverse drug reactions.

In Japan, the approved doses for Foipan® are 100 mg three times daily for postoperative reflux esophagitis and 200 mg three times daily for symptoms of chronic pancreatitis. We propose in the present study dosing at 200 mg po QID, for which Ono has obtained safety data in early clinical trials (see below).⁵ We will ask subjects to space out dosing over 24 hours as much as they can, taking sleep into account.

Much higher doses have been used in some studies without any severe adverse effects, i.e. 9 patients with severe oral carcinomas up to 7.2 g daily for several months as well as a study in healthy individuals of 2 g daily for four weeks.

Since use of the compound in SARS-CoV-2 setting is uncharted territory, we will use doses that are safe within the limits of the SmPC for camostat mesylate. In cell lines, camostat seems able to inhibit the serine-protease mediated maturation of the SARS Spike (S) protein. EC₉₀ is about 5 uM and EC₅₀ about 1 uM in that study. A more recent *in vitro* study showed an EC₅₀ of 0.087 uM (87 NM).⁶ In a mouse model of SARS-CoV-1 (the first SARS) virus, camostat mesylate (30 mg/kg x2) ameliorated progression to acute respiratory distress syndrome (ARDS). The reduction was from 100% to 35% lethality in the mouse model.^{8, 9}

The rationale for the duration of treatment with camostat mesylate (i.e. 200 mg QID daily for 7 days) is in part based on the current treatment guidelines for other lower respiratory tract viral infections and also the known viral kinetics of SARS-CoV-2 in COVID-19 patients. For influenza, the standard recommendation is Tamiflu (oseltamivir 75 mg x 2) for 5 days in adults. Because participants in the proposed camostat trial are enrolled very early after outpatient diagnosis, we anticipate that the majority of them will present with mild to moderate disease. Therefore, we propose to follow the treatment principles for other lower respiratory tract infections of similar disease severity.

2.3 RISK/BENEFIT ASSESSMENT

2.3.1 KNOWN POTENTIAL RISKS

The risks of camostat mesylate (FOIPAN) are based on the package insert provided by Ono Pharmaceuticals for the approved drug.⁵

In the first 7 days of participation in the study, minimal significant risks, either immediate or long-range risks to participants are anticipated from the physical, psychological, social, legal, economic, or other viewpoints by participating in the study that the Principal Investigator (PI) can foresee. Potential risks during the acute phase of COVID-19 infection and coming to the designated facility (outpatient study site) might be infection from others, or study personnel being exposed to active COVID-19 patients. These risks are mitigated by the participants being sampled by experienced staff wearing proper PPE and approved by EH&S during the first week of study participation, during which time they interact with study personnel obtaining respiratory swabs. Study personnel obtaining swabs will be dressed in YNHH system-approved PPE (N95 masks, goggles, face masks, gowns, gloves), and will change gowns, gloves, PPE sleeves between patients, as is standard practice.

At days 14+-2 and 28+-2 days, participants will return to the study clinic and NP swabs and saliva will be obtained. Blood will be drawn for standard blood tests (CBC and chemistries) plus that for research use. A maximum total of 125 mL of blood will be obtained at these two time points.

The guidance for maximum volume of blood draws that will be applied is for non-healthy adults, no more than 2.5% total blood volume in 24-period and no more than 5% total blood volume in 30 days. 70mL/kg must be used to calculate the appropriate blood draw volume per patient. The two blood draws of maximum 125 mL each for a total of 250 over two weeks, plus 30 ccs per visit for Visits 1-4 for a study total of 370ccs is still within the allowable amount.

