8 STUDY ASSESSMENTS AND PROCEDURES

8.1 EFFICACY ASSESSMENTS

Biological specimen collection and laboratory evaluations.

On study days 0, 2 (NP swab optional, saliva required), 4 (NP swab and saliva both required) and 6 (NP swab optional, saliva required), 14+/-2 (NP swab and saliva both required) and 28+/-2, (NP swab and saliva both required), samples will be obtained and analyzed by an FDA-authorized COVID-19 RT-PCR assay coordinated through the YNHH Clinical Virology Laboratory, and Yale Department of Pathology. Additional testing including antigen detection may be done on an NP swab, nasal swab or saliva.

On study days 0, 14+/-2 and 28+/-2, blood will be collected for 1) clinical surveillance→complete blood count, blood chemistries and coagulation including electrolytes, BUN, creatinine, AST, ALT, total and direct bilirubin, HS-CRP, LDH and alkaline phosphatase, PT, INR, d-dimer, fibrinogen; 2) research testing including obtaining serum, plasma and peripheral blood mononuclear cells for research studies. A maximum of 125 mL of blood will be requested to be collected on days 0, 14 and day 28 (total of 375 mL over four weeks) for these purposes.

Respiratory swab and saliva RT-PCR testing will be done by YNHHS or YNHHS-designated send-out laboratories. Quidel's Sofia platform will be use at the study site for antigen detection. Positivity and Ct values will be recorded and \log_{10} viral loads back-extrapolated from \log_{10} being equivalent to 3.3 Ct units or as determined using a concomitant standard curve.

Camostat mesylate in COVID-19 Outpatients

Protocol #2000027971

Version 8.0
18 August 2020

Blood chemistries and CBCs (and an FDA-approved POC urine pregnancy test will be done on site prior to enrollment for appropriate women as required) will be done by YNHHS laboratories and recorded, and results reported to patients.

Remaining blood samples will be stored in a biological specimen repository approved by Yale University as follows:

Investigator: [name]
Type of Review: Modification/Update
Title of Study: Specimen Repository for Hematologic Diseases
IRB Protocol ID: 1401013259
Submission ID: MOD00029770
Committee Name: IRB 0-Ad Hoc Committee

Final Approval Date: 3/29/2020

Expiration Date: 2/17/2021

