8.2 SAFETY AND OTHER ASSESSMENTS

At study visits, vital signs including pulse oximetry will be obtained. Physical examination will not be performed routinely on participants unless dictated by signs or symptoms. Any patient experiencing symptoms requiring medical examination will be referred to hospital..

On all study days, participants will be asked to answer specific questions that relate to known potential adverse effects of camostat mesylate. The previously determined incidence of adverse effects (when drug administered for at least two weeks) are:

Symptom	0.1 to 0.5%	<0.1%	
Rash	0.4		
Pruritus	0.2%		
Gastrointestinal	0.1 to 0.5% (nausea, abdominal discomfort or fullness, diarrhea)	Anorexia, vomiting, dry mouth, heartburn, abdominal pain, constipation	

Included in the informed consent form are concerns about rare side effects. Study personnel will specifically elicit whether there are symptoms concerning for severe allergy such as jaundice, anaphylaxis or anaphylactoid reactions will be determined on a daily basis by study personnel who will ask about such symptoms (yellow eyes, weakness, wheezing, shortness of breath, tongue swelling, hives, rash) during the first 7 days of the study. Laboratory evidence of adverse effects such as thrombocytopenia, hyperbilirubinemia, or hyperkalemia will only be able to be determined at day 14.

Participants will be informed on study day 28 of all available research-specific study results to date. Results that return after day 28 will be communicated with the participant within 2 weeks of such results. If there are actionable results of routine/standard of care lab tests including CBC, chemistries and coagulation studies, they will be reported to participants in a timely manner, otherwise they will be discussed at the day 28 visit or if they become available after day 28, within 2 weeks of when new results become available.

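### Section 2.3.1 clears a 370 mL blood total with no weight condition, although its own 30-day cap allows that volume only from about 105.7 kg; Section 8.1 and the schedule list different draws

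*Combined protocol and SAP*

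**What the plan says.** Section 2.3.1 (Known Potential Risks) sets the limit as "no more than 2.5% total blood volume in 24-period and no more than 5% total blood volume in 30 days", and adds that "70mL/kg must be used to calculate the appropriate blood draw volume per patient". It then counts two draws of up to 125 mL each, at days 14 and 28, "plus 30 ccs per visit for Visits 1-4", and concludes "for a study total of 370ccs is still within the allowable amount". No body weight is attached to that conclusion. The preceding paragraph of the same section gives 125 mL as the combined maximum for days 14 and 28, which does not agree with 125 mL for each.

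Section 8.1 (Efficacy Assessments), which tells staff what to collect, says: "A maximum of 125 mL of blood will be requested to be collected on days 0, 14 and day 28", with a "total of 375 mL over four weeks". It refers to neither limit nor to body weight.

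The Schedule of Activities (Section 1.3) marks hematology and coagulation, chemistries, and "Blood for research biorepository" at days 0, 14 and 28 only. The one other blood item is a pregnancy test at day 14, as indicated. Nothing is marked for blood at days 2, 4 or 6. Sections 5.1 and 5.2 set no minimum weight for entry.

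**The concern.** A percentage of blood volume at a fixed mL/kg is a weight-dependent limit, so a fixed total in mL can be declared acceptable only together with a weight. Section 2.3.1 gives none, and the weight that its total implies is above that of many adults who could enroll.

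The volume that 2.3.1 clears is also not the volume that 8.1 asks staff to request. Someone working from 8.1 sees 125 mL on three days and no limit. Someone who turns to 2.3.1 is told that the maxima pass. Neither place prompts the per-patient calculation that would reduce the draw for a lighter participant. What is at stake is compliance with the protocol's own limit for people who are acutely ill. No endpoint, power calculation or efficacy analysis depends on it.

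**Working it through.** **Inputs.** From 2.3.1: limits of 2.5% per 24 hours and 5% per 30 days, 70 mL/kg, two draws of 125 mL and four of 30 mL. From 8.1: three draws of 125 mL.

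**The plan's own total.** 2 x 125 + 4 x 30 = 250 + 120 = 370 mL. This reproduces 2.3.1. For 8.1, 3 x 125 = 375 mL, which also reproduces.

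**Limits per kg.**
- 24 hours: 0.025 x 70 = 1.75 mL/kg
- 30 days: 0.05 x 70 = 3.5 mL/kg

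**Lowest weight at which each maximum is allowed** (volume divided by limit).
- 370 mL in 30 days: 370 / 3.5 = 105.7 kg
- 375 mL in 30 days: 375 / 3.5 = 107.1 kg
- One 125 mL draw in 24 hours: 125 / 1.75 = 71.4 kg

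**At example weights.** These are illustrative, because the documents give no weight distribution.

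| Weight | 24-hour limit | 30-day limit | 370 mL as % of 30-day limit | 375 mL as % of 30-day limit |
|---|---|---|---|---|
| 60 kg | 105 mL | 210 mL | 176% | 179% |
| 70 kg | 122.5 mL | 245 mL | 151% | 153% |
| 80 kg | 140 mL | 280 mL | 132% | 134% |
| 100 kg | 175 mL | 350 mL | 106% | 107% |

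**Draw lists side by side.**

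| Visit | Section 2.3.1 | Section 8.1 | Schedule (1.3) |
|---|---|---|---|
| Day 0 (Visit 1) | 30 mL | up to 125 mL | blood marked |
| Days 2, 4, 6 (Visits 2-4) | 30 mL each | none | none |
| Day 14 | up to 125 mL | up to 125 mL | blood marked |
| Day 28 | up to 125 mL | up to 125 mL | blood marked |
| Total | 370 mL | 375 mL | no volumes given |

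The totals differ by only 5 mL, but they are built from different draws. Of the 370 mL in 2.3.1, 3 x 30 = 90 mL falls at visits where neither 8.1 nor the schedule has a draw.

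**How the two limits interact.** Two draws at the full 24-hour limit use 2 x 1.75 = 3.5 mL/kg, which is the whole 30-day allowance. Under 8.1's three equal maxima, a participant at or below 71.4 kg drawn to the 24-hour limit on days 0 and 14 has nothing left for day 28 while day 0 is still inside the 30-day window. The correction therefore has to say which blood is reduced.

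**The case against.** The strongest reply is that the paragraph already contains a binding rule. Volumes must be calculated per patient at 70 mL/kg, and the 125 mL figures are maxima, worded in 8.1 as an amount to be requested. Read together, the sections allow no one to be drawn above the limits, and lighter participants simply give less. A rule stated once in 2.3.1 need not be repeated in 8.1 to apply. This stands, and it is why the point is minor. It does not make the unconditional conclusion in 2.3.1 true, and it does not settle which draw list applies.

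Two lenient readings also deserve a check.
- If the last visit falls on day 30 and day 0 is treated as outside the window, the 2.3.1 total drops to 370 - 30 = 340 mL, which still needs 340 / 3.5 = 97.1 kg. The 8.1 total drops to 250 mL, which needs 71.4 kg.
- If 125 mL is taken as the combined maximum for days 14 and 28, the total is 125 + 120 = 245 mL, which needs 245 / 3.5 = 70 kg. The sentence that makes the check, however, counts 125 mL for each draw.

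Under neither reading does the statement hold without a weight condition.

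A reader might go further and infer that every participant under 105.7 kg would be over-drawn, or that the 370 mL sentence is the protocol's only safeguard on blood volume. The documents support neither inference: the operative safeguard is the per-patient calculation. Nor can it be said that scheduled safety laboratory tests would be lost, because no section divides the 125 mL between clinical and research use.

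**Conclusion.** The concern holds in a limited form. At its stated maxima, the conclusion in 2.3.1 is wrong for participants under 105.7 kg. The 8.1 total is allowable only from 107.1 kg, and one full draw breaks the 24-hour limit below 71.4 kg. Sections 2.3.1 and 8.1 conflict on day 0 (30 against 125 mL) and on Visits 2-4 (30 mL each against none). The schedule agrees with 8.1 on draw days, and 2.3.1 is inconsistent within itself on the day 14 and day 28 volume.

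These thresholds assume that all draws fall inside one 30-day window, as they do at nominal visit timing, and that each draw is taken at its maximum. A breach of the limit is possible rather than certain. Severity is minor: it concerns the accuracy of a participant-safety statement and the consistency of collection instructions, with no effect on efficacy.

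**What to change.** 1. In 2.3.1, replace the blanket conclusion with the weight-dependent limit: at most 1.75 mL/kg in 24 hours and 3.5 mL/kg in 30 days. Resolve whether 125 mL is per draw or combined for days 14 and 28.
2. In 8.1, state that each draw is at most the lesser of 125 mL and 1.75 mL/kg, and that the running 30-day total is at most 3.5 mL/kg. Say that research volume is reduced first, so that the scheduled safety tests are kept.
3. Align 2.3.1, 8.1 and the schedule: choose 30 or 125 mL for day 0, and either schedule the Visit 2-4 draws or remove them from 2.3.1.
4. If equal draws at days 0, 14 and 28 are offered as an option, use at most 1.16 mL/kg each (3 x 1.16 = 3.48). Rounding 3.5 / 3 up to 1.17 gives 3.51 mL/kg, just over the limit.

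The cost is a wording amendment with the usual IRB review. Weight is already measured at every visit under the schedule, so no new procedure is needed. Any reduction in research blood at lower weights already follows from the existing rule in 2.3.1 and is not a cost of this change.
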